#### 485 **3.d Preparation and Administration of Study Drug**

Gabapentin (300 mg per capsule) and placebo will be supplied to patients in identical 486 487 opaque capsules in blinded fashion. The medications will be distributed in 4 separate 488 vials representing each of the four weeks of the Titration Period and distributed in 8 489 separate vials prior to the Fixed-Dose period.

#### 490 **3.**e **Subject Compliance Monitoring**

491 There will be check-ins with the study participants every two weeks conducted virtually 492 through the participant's preferred communication method (i.e. phone call or video call) 493 to answer questions and ensure participants are adhering to medication schedule. Subjects 494 will be asked to keep a paper calendar for daily notes of pill count, side/adverse effects,

495 and study barriers. The paper calendar will be mailed back to the RA after study 496 completion.

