#### 207 *C1* **Primary** Aim

208 To evaluate the efficacy of oral gabapentin on improvement of olfactory dysfunction in 209 patients with post-COVID-19 anosmia, hyposmia, or parosmia. Participants will receive a 210 maximum of 14weeks of either gabapentin or placebo with the first four weeks serving as 211 a titration phase and the last two weeks serving as a taper-down period.

212 *C2* Secondary Aim

213 Describe the adverse effects of gabapentin. All participants will be monitored for adverse 214 effects throughout the study.

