### 341 E1 Overview or Design Summary

This study will be a double-blinded, placebo-controlled, randomized pilot clinical trial to evaluate the efficacy of gabapentin to improve post-COVID-19 olfactory dysfunction.

- 344 This study will also describe adverse effects related to oral gabapentin use.
- 345

This study will be conducted via virtual research guidelines and procedures. We will not require in-person patient participation or evaluation. Following initial evaluation to ensure potential participants meet all inclusion criteria and none of the exclusion criteria,

the research study will be explained in full via Zoom call, phone call if necessary.

350 Participants will then be randomized in a 1:1 allocation via permuted-block sequencing

into the oral gabapentin group or the placebo group. All assessments will be conductedthrough a HIPAA-compliant online survey form. Baseline assessments will help us

determine subjective and objective rates of olfactory dysfunction. Assessments will be

354 conducted again after the 8-week Fixed-Dose period and 4 weeks after completing taper.

355 356	The primary objective of this study is to assess the efficacy of oral gabapentin in improving olfactory dysfunction secondary to COVID-19.
357	E2 Subject Selection and Withdrawal
358	
359	2.a Inclusion Criteria
360	Participants will be recruited based on the following inclusion criteria:
361	- Men and women between the ages of 18 and 65 years
362	- Residing within the states of Missouri or Illinois
363	- Clinically diagnosed or subjective olfactory dysfunction (anosmia, hyposmia,
364	or parosmia) of at least 3 months duration associated with COVID-19
365	infection

- 366- initial UPSIT score consistent with diminished olfactory function (score  $\geq 6$ 367and  $\leq 33$  in men and score  $\geq 6$  and  $\leq 34$  in women).
- Willing to respond daily to study surveys, preferably through smartphone with
   unlimited texting plan.
- In possession of all 7 household items associated with *NASAL-7*: soap, burnt
  candle, peanut butter, herb, garlic, lemon, and coffee

373 2.a Exclusion Criteria

Individuals will not be allowed to participate in this study if they meet one or more of thefollowing exclusion criteria:

- Clinically diagnosed olfactory dysfunction secondary to non-COVID-19 viral
   infection, genetic abnormalities or congenital dysfunction, trauma, nasal
   polyps, neurodegenerative disorders
- 379
  380

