### 587 Gabapentin (300 mg pill) Titration Schedule

588

586

589 If at any point during the Titration Period, the participant wishes to discontinue 590 the medication for any reason, they will be instructed to follow the taper down schedule 591 (see below) in order to safely stop the medication. The participant will be informed that 592 any abrupt stoppage of gabapentin could cause serious adverse effects.

Participants will be contacted by telephone or video call by the Research Assistant
(RA) at the end of Titration period. The purpose of this call will be to query the
participants about adverse effects. Participants will be provided with a paper calendar
and asked to maintain diaries of olfactory and taste symptoms and adverse effects
possibly related to the intervention.

598 Participants will not complete any forms at the completion of Titration period.599 Instead, they will proceed directly to Fixed-Dose Period.

### 600 601

Fixed-Dose Period: duration 8 weeks

602During the Fixed-Dose period, participant's dose will remain at their maximum tolerated603dosage established during the Titration phase. The study drug will be distributed in eight604separate vials representing the eight weeks of the Fixed-Dose period. The RA will605contact the participants at the end of Week 4 to administer the blind assessment using606REDCap (survey titled: "Blind Assessment"). Participants will complete the following607forms after completing the Fixed-Dose Period (survey titled: "FixedDoseSurvey"):

- 608
- 609 1.) Clinical Global Impression of Severity Scale (CGI-S).

610 2.) Clinical Global Impression of Improvement Scale (CGI-I)

- 611 3.) University of Pennsylvania Smell Identification Test (UPSIT)
- 612 4.) Olfactory Dysfunction Outcomes Rating (ODOR)
- 613 5.) *NASAL-7*
- 6.) *Clinical Global Impression-Severity Scale for Parosmics (CGI-P)*
- 615 7.) Adverse Event assessment
- 616 8.) Compliance
- 617

618 *Adverse events*. Any unintentional or unfavorable clinical sign or symptom, any new

619 illness or disease or the deterioration of existing disease or illness, or any clinically

620 significant deterioration in any laboratory assessments or clinical tests while participating

621 in this study will be captured. The study coordinator will contact participants virtually to

622 answer questions and assess adverse effects after Titration period, Fixed-Dose period,

- 623 and 4 weeks after Taper.
- 624

- 625 Taper Down: maximum duration 2 weeks

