## 766 F4 Study Outcome Measurements and Ascertainment

Participants will complete an assessment of blind after completion of 4 weeks of
the 8-week Fixed-Dose period using REDCap (survey titled: "Blind Assessment")

Participants will also complete the following forms using REDCap (survey titled
"FixedDoseSurvey") after completing the 8-week Fixed-Dose Period:

772 773

1.) Clinical Global Impression of Severity Scale (CGI-S).

7742.) Clinical Global Impression of Improvement Scale (CGI-I)

- 7753.) University of Pennsylvania Smell Identification Test (UPSIT)
- 4.) Olfactory Dysfunction Outcomes Rating (ODOR)
- 777 5.) *NASAL-7* 
  - 6.) Clinical Global Impression-Severity Scale for Parosmics (CGI-P)
- 779 7.) Adverse Event assessment
- 780 8.) Compliance
- 781

782	Participants will also complete the following forms using REDCap (survey titled		
783	FinalSurvey) 4 weeks after completing the Taper Period.		
784	1)	Clinical Global Impression of Severity Scale (CGI-S).	
785	2)	Clinical Global Impression of Improvement Scale (CGI-I)	
786	3)	University of Pennsylvania Smell Identification Test (UPSIT)	
787	4)	Olfactory Dysfunction Outcomes Rating (ODOR)	
788	5)	NASAL-7	
789	6)	Clinical Global Impression-Severity Scale for Parosmics (CGI-P)	
790			
791			

792 G Statistical Plan

793

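### Eligibility requires willingness to answer daily surveys that the available text never describes, and the only day-by-day pill and side-effect record is a paper calendar with no interim capture and no stated return route for leavers

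*Combined protocol and SAP*

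**What the plan says.** **Eligibility.** E2 2.a (Inclusion Criteria) lists "Willing to respond daily to study surveys, preferably through smartphone with" an unlimited texting plan.

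**Surveys.** E1 places the post-baseline assessments at two times, "conducted again after the 8-week Fixed-Dose period and 4 weeks after completing taper". F4 adds one survey: "Participants will complete an assessment of blind after completion of 4 weeks of" the 8-week Fixed-Dose period. For the end of titration, F2 says "Participants will not complete any forms at the completion of Titration period". K1 names Screening Survey, Screening UPSIT, Week0BaselineSurvey, Blind Assessment, FixedDoseSurvey and FinalSurvey.

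**Daily record.** Under E3 3.e, subjects "will be asked to keep a paper calendar for daily notes of pill count, side/adverse effects" "and study barriers. The paper calendar will be mailed back to the RA after study" completion. The titration text in F2 also describes a paper calendar, but with different content: smell and taste symptoms and adverse effects, with no mention of pill counts.

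**Leavers.** E2 2.g provides an exit interview that asks about adverse effects. E2 2.h limits data on leavers to that interview and whatever was collected beforehand, and adds that data collected up to that point will be left out of the analysis. Neither section mentions the calendar.

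**Use.** The only secondary aim (C2) is "Describe the adverse effects of gabapentin. All participants will be monitored for adverse" effects throughout the study.

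**The concern.** Two parts of the plan do not fit together. The eligibility rule selects people for daily electronic reporting, and the data collection then makes no use of it. The daily information goes instead onto paper that staff are not scheduled to see until the end.

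Two things are at stake. First, a willing and otherwise suitable person could be excluded for declining a task that is not in the protocol. Second, the dated detail on side effects and capsules taken is what gives a description of adverse effects its onset, duration and relation to dose. It arrives late for completers and has no stated way in for leavers. People who stop because of side effects carry much of the information for that aim.

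**Working it through.** **Step 1: is any described survey daily?** The criterion in E2 2.a was set against the instruments in K1 and their timing in F1, F2 and F4.

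| Instrument | When |
|---|---|
| Screening Survey | once, before eligibility |
| Screening UPSIT | once, before consent |
| Week0BaselineSurvey | once, at baseline |
| Blind Assessment | once, after 4 weeks of the Fixed-Dose period |
| FixedDoseSurvey | once, after the Fixed-Dose period |
| FinalSurvey | once, 4 weeks after taper |

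Daily instruments: 0 of 6. The flow chart in F2 is not shown, so a daily survey there cannot be wholly excluded, but K1 is the plan's own list and names none.

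**Step 2: how late is the calendar?** From F3 3.a, titration (up to 4 weeks) + Fixed-Dose (8) + taper (2) + follow-up (4) = 18 weeks, and 18 × 7 = 126 days. This takes study completion to mean the final contact. If it meant the end of taper, the figure would be 4 + 8 + 2 = 14 weeks, or 14 × 7 = 98 days. A day-1 entry is thus first seen about 14 to 18 weeks later at full duration, unless someone asks for it sooner.

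**Step 3: how many leavers?** G1 gives 60 enrolled, 33% dropout and 40 evaluable. The plan's figure reproduces: 60 × (1 − 0.33) = 40.2, or 40. Planned leavers are 60 − 40 = 20, one third of those enrolled. E2 2.f to 2.h give no route for returning their calendars, so 20 is the most that the planning figure puts at risk.

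**Step 4: could existing contacts close the gap?** E3 3.e schedules check-ins every two weeks. If they run through treatment, that is 14 / 2 = 7 contacts; if through follow-up, 18 / 2 = 9. Their stated purpose is to answer questions and support adherence. Nothing says calendar entries are read out or recorded, so the contacts exist but are not used for this.

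**Step 5: does any planned analysis depend on the calendar?** The primary outcome is CGI-I, collected in REDCap. G3 contains no analysis of pill counts, dose taken or per-protocol status. The calendar therefore bears on the descriptive secondary aim and on adherence, not on the efficacy comparison.

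**The case against.** The strongest reply is that little rests on the calendar.

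- **Adverse effects** are also collected by coordinator contacts after titration, after the Fixed-Dose period and 4 weeks after taper; by an item in FixedDoseSurvey; by the exit interview; and by safety follow-up to 30 days after stopping drug (E2 2.g, although 2.h rules out other follow-up of leavers). Participants can reach the team at any hour (F3).
- **Adherence** is also covered by the two-weekly check-ins, a compliance item in FixedDoseSurvey and a query about the taper.
- **The criterion** may be loose wording for the daily calendar notes.
- **Leavers** are paid in proportion to work done (I1), which gives some reason to return the calendar.
- **A daily electronic form** has a cost. Over 98 treatment days it is 98 × 60 = 5,880 forms at full participation, against G4's stated wish to keep assessments few and simple.

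Most of this stands. A reader might infer that safety during titration cannot be watched, or that the secondary aim depends on the calendar alone. The documents do not support either inference, because the other sources operate throughout. A reader might also infer that the primary result is compromised through unknown dose taken, but no analysis in G3 uses that information.

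The reply does not remove the core of the point. The other sources are periodic and rely on recall or volunteered reports. F3 3.c says adverse events are abstracted from source documentation. In a trial without required in-person evaluation, the calendar is the only day-by-day source described for non-serious events and their dates. If the criterion is only loose wording, it still needs correcting, because it governs who may enter.

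**Conclusion.** The point holds as a modest but real gap. The available text contains an eligibility requirement with no matching procedure: 0 of 6 listed instruments are daily. The only daily record of capsules and side effects is seen about 14 to 18 weeks after its first entry, and no recovery from leavers is stated. The effect is limited to later and less complete dated detail on adverse effects and adherence; the primary CGI-I analysis is untouched.

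The figure of about 20 of 60 could be read as a forecast of lost calendars. It is not one: it is the plan's allowance for non-evaluable participants, with no stated link to side effects or to calendar return. The number of people who would be excluded by the criterion cannot be known from the documents.

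The conclusion assumes that the flow chart, which is not shown, adds no daily survey, and that check-ins do not already transcribe the calendar as an unwritten practice.

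**What to change.** 1. **E2 2.a:** delete the daily-survey criterion, or reword it as willingness to keep the daily calendar.
2. **E3 3.e:** capture the calendar at each existing two-weekly check-in, by photograph or by a read-out entered in REDCap. Do the same at the exit interview for anyone who leaves. The paper original is still mailed back.
3. **E3 3.e and F2:** settle one list of calendar content. One text names pill count, side effects and barriers; the other names smell and taste symptoms and adverse effects.
4. **E2 2.h:** reconcile with C2 and 2.g, so that adverse-effect data from leavers, including calendar entries, are used in the safety description.

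The cost is a few minutes more per check-in and a short REDCap entry or upload. No outcome, sample size or treatment schedule changes. A daily REDCap survey would also resolve the mismatch, but it adds burden and is optional.

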#### 497 **3.**f **Prior and Concomitant Therapy**

Patients receiving concomitant therapy specifically for the treatment of olfactory 498 499 dysfunction will not be eligible for the trial unless they are able to stop taking those 500 therapies during the conduct of the study. Participants who have tried previous therapies 501 for their olfactory dysfunction, including over-the-counter treatments such as vitamin A 502 or omega-3 fatty acids will be eligible for the trial. Information will be gathered on their 503 use of prior or current therapies, and if needed, a sensitivity or subgroup analysis may be 504 considered.

505

### 506 3.g Packaging

507 The Research Pharmacist will deliver the gabapentin and placebo in a blinded fashion to 508 the research assistant for distribution to the participants via FedEx.

#### 509 3.h **Blinding of Study Drug**

510 Participants will be divided into two groups; one group will be given oral gabapentin

- 511 while the other group will be given oral placebo. The research pharmacist will receive the
- 512 randomization assignment code from the biostatistician. The RA will pick up the study
- 513 drug in blinded fashion from research pharmacist and distribute it to the participant via
- 514 FedEx delivery. In this way, only the Research Pharmacist will know participant
- 515 assignment. Adequate taper of gabapentin will be provided for those on gabapentin while
- 516 the placebo group will receive additional placebo for taper in order to maintain the blind.

### 517 3.i Receiving, Storage, Dispensing and Return

518 The services of the Investigational Pharmacy at Barnes-Jewish Hospital will be used for 519 this trial. The product used in this trial will be managed by the pharmacist according to

- 520 the pharmacy SOP.
- 521
  - **F** Study Procedures
- 522

### 523 F1 Screening for Eligibility

524 Individuals who reach out with interest in the study after seeing the approved study flyer or who have contacted RA for participation in similar studies for which recruitment has 525 ended will asked to complete an online screening questionnaire (survey titled: 526 527 "ScreeningSurvey") to ensure he or she meets all the inclusion criteria and does not meet any exclusion criteria. Following eligibility confirmation, the RA will collect information 528 529 required to mail screening smell identification test (UPSIT). Once received, the 530 participant will complete the UPSIT and provide their response virtually through the 531 REDCap survey. Once eligibility is confirmed based on UPSIT score, participants will 532 be provided through REDCap an online consent form to review and complete. The RA 533 will offer each participant the option to review the consent form independently or with the RA via zoom or phone call (zoom as the preferred option). Once the participant 534 535 electronically signs the consent form, the RA will review it and sign. The REDCap 536 software will automatically email the participant a copy of their completed form.

[figure not shown]
### 537 F2 Schedule of Measurements

538 Following the recruitment period and successful enrollment, baseline survey completion

(survey titled Week0BaselineSurvey) and randomization of participants will occur. The
 timeline for measurements can be seen below.

541

### 542 Gabapentin Study Flow Chart

549	
550	
551	
552	
553	
554	a. Federal guidelines require timely reporting (within 15 calendar days) of an
555	unanticipated or life-threatening event or death occurring within 30 days of
556	active study participation.
557	
558	
559	Titration Period: maximum duration 4 weeks
560	
561	Placebo. In this study, we plan to use an inert placebo and not an active drug
562	or non-active drug with side effects similar to gabapentin. Participants randomized to the
563	Placebo arm will participate in a 4-week Titration Period. Placebo will be supplied to
564	patients in opaque capsules in blinded fashion. The medications will be distributed in 4
565	separate vials representing each of the four weeks of the Titration Period. If intolerable
566	adverse reactions occur, the dosage will be decreased to prior tolerable dose.
567	Gabapentin. Participants randomized to the gabapentin arm will take
568	gradually titrated dosages of gabapentin as follows:
569	
570	Week 1, 900 mg/d (300 mg TID)
571	Week 2, 1800 mg/d (600 mg TID)
572	Week 3, 2700 mg/d (900 mg TID)
573	Week 4, 3600 mg/d (1200 mg TID)
574	
575	Gabapentin (300 mg per capsule) will be supplied to participants in opaque
576	capsules in blinded fashion identical to the supply of Placebo. The medications will be
577	distributed in 4 separate vials representing each of the four weeks of the Titration Period.
578	All participants' dosages will be titrated to a maximum dose of 3600 mg/d, regardless of
579	any effect achieved at lower dosages. If intolerable effects occur, dosage will be
580	decreased by 1 dose (300 mg) step (e. g. if 2700 mg/d is intolerable, dosage will be
581	decreased to 2400 mg/d). Further de-escalation will be determined by PI clinical
582	judgement to prior tolerable dose. Participants with intolerable effects may have a lower
583	maximum dose than 3600mg/d and may complete the Titration Period in less than 4
584	weeks. The dose established during the Titration Period will be maintained throughout
585	the Fixed-Dose period.

WEEK 1	WEEK 2	WEEK 3	WEEK 4
900 MG	1800 MG	2700 MG	3600 MG
1 MORNING 1 NOON 1 NIGHT (21 PILLS)	2 MORNING 2 NOON 2 NIGHT (42 PILLS)	3 MORNING 3 NOON 3 NIGHT (63 PILLS)	4 MORNING 4 NOON 4 NIGHT (84 PILLS)

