### 301 D3 Dose Rationale and Risk/Benefits

Gabapentin dosing for this study mirrors dosing for the prior study "Relief of Idiopathic
 Subjective Tinnitus" (IRB #02-0717)

- Following randomization, participants in the gabapentin arm will take gradually titrated dosages in order to achieve a dose of 3600mg/d or highest tolerable dose. The titration schedule will span a maximum 4 weeks to reach 3600mg/d.
- 307 Week 1, 900 mg/d
- 308 Week 2, 1800 mg/d
- 309 Week 3, 2700 mg/d
- 310 Week 4, 3600 mg/d
- 311

312	Gabapentin (300 mg per capsule) and placebo will be supplied to patients in
313	identical opaque capsules in blinded fashion. The medications will be distributed in 4
314	separate vials representing each of the four weeks of the Titration Period. All
315	participants will be provided an equal number of capsules and instructed to follow a TID
316	(i.e., 3 times per day) dosing schedule. All participants' dosages will be titrated to a
317	maximum dose of 3600 mg/d, regardless of any possible beneficial effect achieved at
318	lower dosages. If intolerable adverse reactions occur, the dosage will be decreased to
319	previous tolerable dose (e.g. if 2700mg/d is intolerable, dosage will be decreased to 1800
320	mg/d). If, during the first week, 900 mg/d is intolerable, dosing will be decreased by 300
321	mg/d per day until tolerable (i.e., 600 mg/d, 300mg/d) or until they are no longer taking
322	the medication. The dose established during the Titration Period will be maintained
323	throughout the Fixed-Dose period. Participants receiving the matching placebo capsules
324	will be provided similar instructions for titration and de-escalation, should side effects
325	develop.
326	-

The potential benefit to the participant is improvement of their olfactory dysfunction
using this therapy. The potential benefit to the society is the use of the pilot study results
to initiate a larger trial to further evaluate the efficacy of gabapentin in the treatment of
post-COVID-19 olfactory dysfunction.

331

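### Section F2 words the dose step-down differently for each arm, contradicting D3; blinded staff cannot apply it, and following it by arm could expose allocation in some participants.

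*Combined protocol and SAP*

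**What the plan says.** Section F2 (Titration Period) treats the arms in separate paragraphs. Under placebo, if intolerable "adverse reactions occur, the dosage will be decreased to prior tolerable dose"; no worked example is given. Under gabapentin, the dose is "decreased by 1 dose (300 mg) step (e. g. if 2700 mg/d is intolerable, dosage will be" "decreased to 2400 mg/d). Further de-escalation will be determined by PI clinical" judgement, back to a dose tolerated before. Section E3, 3.b (Treatment Regimen) repeats the 300 mg step for the gabapentin arm.

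Section D3 gives another rule: an intolerable 2700 mg/d goes to 1800 mg/d, and an intolerable 900 mg/d in week 1 falls in 300 mg/d reductions. It adds that those on placebo "will be provided similar instructions for titration and de-escalation, should side effects" develop.

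On blinding, 3.h describes pharmacist-to-assistant handover and "FedEx delivery. In this way, only the Research Pharmacist will know participant" assignment. F2 fixes the stepped-down dose for the rest of treatment: "weeks. The dose established during the Titration Period will be maintained throughout" the Fixed-Dose period, which lasts 8 weeks. The primary outcome (C3) is a self-rated CGI-I at the end of that period, with minimal improvement or better counted as response.

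**The concern.** Two problems follow from the F2 wording.

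First, it cannot be carried out under the blind. The rule turns on the arm, but the PI and research assistant do not know the arm. G5 reserves unblinding for safety concerns, and section F3 removes a participant whose blind is broken for a serious or unexpected adverse event. No section gives the pharmacist a part in step-down decisions. An ordinary dose reduction therefore has no route to the information the rule needs.

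Second, if the two rules were nonetheless followed by arm, the number of capsules taken each day would differ between arms after the same event. D3's equal supply of capsules hides the number supplied, not the number taken. Under 3.e participants note a daily pill count, staff check adherence every two weeks, and the calendar goes to the research assistant after completion. The people concerned are those with side effects, in a trial whose placebo is deliberately inert, so they already have one cue to their allocation. The primary outcome is their own rating. With the 20 evaluable per group planned in G1, one changed rating moves a group's response rate by 1/20 = 5 percentage points.

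**Working it through.** **Inputs**
- Capsule strength, F2: "Gabapentin (300 mg per capsule) will be supplied to participants in opaque" capsules, with placebo supplied identically.
- Titration levels, F2: 900, 1800, 2700 and 3600 mg/d.
- Week 3 schedule, F2: "3 MORNING 3 NOON 3 NIGHT (63 PILLS").
- Gabapentin first step, F2 and 3.b: minus 300 mg/d.
- Placebo step, F2: back to the prior tolerable dose. F2 does not define this. I assume it means the previous titration level, as in D3's 2700 to 1800 example.

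**Reproducing the plan's own figures**

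Capsules per day = mg/d ÷ 300; capsules per week = 7 × capsules per day.
- 900 ÷ 300 = 3 a day, 21 a week
- 1800 ÷ 300 = 6 a day, 42 a week
- 2700 ÷ 300 = 9 a day, 63 a week
- 3600 ÷ 300 = 12 a day, 84 a week

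These match the F2 titration table. The F2 example also reproduces: 2700 − 300 = 2400 mg/d, or 8 capsules.

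**First step-down, F2 applied by arm**

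| Level not tolerated (capsules/day) | Gabapentin paragraph | Placebo paragraph (D3 meaning) |
|---|---|---|
| 12 | 12 − 1 = 11 | 9 |
| 9 | 9 − 1 = 8 | 6 |
| 6 | 6 − 1 = 5 | 3 |
| 3 | 3 − 1 = 2 | no level given in F2 |

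**What each count would reveal**
- 11, 8 or 5 a day: not a titration level, and on this reading not reachable from the placebo paragraph. It would point to gabapentin.
- 9, 6 or 3 a day: reachable on placebo in one step, but also on gabapentin, because F2 allows further de-escalation to an earlier tolerated dose. Not informative by itself.
- 2 a day: not exclusive to gabapentin. D3 allows 300 mg/d reductions from 900 mg/d and extends similar instructions to placebo.

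**The same event across sections, starting from 2700 mg/d**
- D3: 1800 mg/d, with similar instructions for placebo.
- E3, 3.b: 2400 mg/d, gabapentin arm.
- F2, gabapentin paragraph: 2400 mg/d, then PI judgement.
- F2, placebo paragraph: prior tolerable dose, no figure.

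**Taper table in F2**

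Its columns are 3600, 2700, 1800 and 900 mg. The doses that one 300 mg step produces are 3300, 2400, 1500 and 600 mg/d, and none has a column.

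**Under a single rule**

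Whatever step is chosen, the same starting level then gives the same count in both arms, so the rule itself adds no information about assignment.

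**The case against.** The best counter-argument is that F2 is loose drafting of one intended rule. D3 promises placebo participants similar instructions. In F2 the sentence just before the 300 mg step speaks of all participants' dosages, the step sentence itself names no arm, and the gabapentin paragraph ends with the same fallback phrase as the placebo one. This is a plausible account of what was meant, and it stands as a reason not to read F2 as a deliberate design. It does not settle the matter, because D3's own figure (1800) conflicts with 3.b and F2 (2400) and no section says which governs.

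It is also fair to say that the separation of counts takes the placebo meaning from D3 while not applying D3 to gabapentin. If D3 governed both arms, 9 a day would become 6 in each and the difference would vanish. That is why the result is stated only conditionally.

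Third, blinded staff who cannot know the arm may simply give everyone the same instruction, in which case the count carries nothing about allocation. No section hands the decision to the pharmacist, and none says participants are told two rules. This too stands.

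The blind assessment after 4 weeks of the Fixed-Dose period might help to show a loss of blinding. It would not prevent one.

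**Conclusion.** The contradiction is established: F2 words the step-down by arm, D3 and 3.b give different figures, and staff blinded under 3.h cannot apply the F2 text as it stands.

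The consequence for the blind is conditional. It needs three things: the F2 wording is actually followed by arm; the placebo phrase means the previous titration level; and the observer or participant knows the rule. If all hold, a count of 11, 8 or 5 capsules a day after a first step-down points to gabapentin. Counts of 9, 6, 3 or 2 do not identify the arm.

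A reader might infer that the plan unblinds everyone who steps down, or that the two sets of counts never overlap. The documents do not support either, for the reasons shown at 9, 6, 3 and 2 a day. A reader might also attach a headcount: assuming 20% to 40% of 30 gabapentin participants step down would give 30 × 0.20 = 6 to 30 × 0.40 = 12. The documents give no step-down rate, and that range would also require all three conditions and that each person stays at an identifying count. The number affected cannot be computed.

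**What to change.** Reconcile D3, E3 3.b and both F2 paragraphs into one step-down rule. State it once, in capsules, for every participant, with no mention of arm, and have the other sections refer to it. It should cover every titration level, including the lowest, and any role for PI judgement should apply to all participants alike. Then check that the F2 taper table covers every dose level the rule can produce. Which step is used, and how the additional levels are tapered, is for the clinical team to decide.

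The cost is protocol wording, carried through to participant instructions. The capsules stay the same, and neither the sample size nor the analysis changes.
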